7.5 Efficacy

The primary endpoint is related to safety and there are no primary efficacy endpoints. Analysis methods for the primary safety endpoint are described in [Section 7.6.1](#). Descriptive analyses of secondary endpoints will be performed to evaluate the hypothesis of similar efficacy between the treatment arms A and B.

7.5.1 Objective Response Rate

ORRs (based on investigator assessments using RECIST 1.1 criteria) and corresponding 95% exact CIs will be calculated using the Clopper Pearson method⁸ for each of the treatment arms. BOR will be tabulated for each treatment group. The 2 treatment arms A and B will be compared using a two-sided Cochran-Mantel-Haenszel (CMH) test, stratified by PD-L1 expression and M stage at screening (IVRS source). Associated odds ratios and 95% CIs for Arm A relative to Arm B will be calculated, and a p-value will be presented for descriptive purposes. An estimate of the difference in ORRs between Arms A and B and corresponding 95% CI will be calculated using CMH methodology, adjusting for the stratification factors PD-L1 expression and M stage at screening.

Sensitivity Analysis (Arms A and B only)

Similar analyses of ORR will be performed using the following modification:

- ORR using the strata as determined at baseline (CRF source for M-stage, clinical database for PD-L1). This analysis will be performed only if the IVRS value for one stratification factor differs from the baseline value in at least 10% of treated subjects.

Subgroup Analysis (Arms A and B only)

To assess consistency of treatment effects in ORR in different subsets, a “forest” plot of the unweighted differences in ORRs and corresponding exact 95% CIs using the Newcombe method⁹ will be produced for the following variables:

- PD-L1 Status ($\geq 5\%$ expression and $< 5\%$ expression/indeterminate) (source: clinical database)
- BRAF mutation status (BRAF mutant and wildtype)
- M Stage at Study Entry (M0/M1a/M1b and M1c) (source: CRF)
- Age category I (< 65 and ≥ 65)
- Age category II (< 65 , ≥ 65 - < 75 , and ≥ 75)
- Gender (male and female)
- Race (white, black, asian, and other)
- Region (EU, Non-EU)
- Baseline ECOG Performance Status (0 and 1)
- History of Brain Metastases (Yes and No)
- Baseline LDH (\geq ULN and $>$ ULN)

- Baseline LDH ($\leq 2 \times \text{ULN}$ and $> 2 \times \text{ULN}$)
- AJCC Stage (III and IV)

If a subgroup category has less than 10 subjects per treatment group, ORR will not be computed/displayed.

For purposes of analysis, countries will be included in each region category according to Table 7.5.1-1.

Table 7.5.1-1: Region Definition

Country	Region
Denmark	EU
France	EU
Germany	EU
Italy	EU
Netherlands	EU
Poland	EU
Spain	EU
United Kingdom	EU
Australia	Non-EU
Canada	Non-EU
Israel	Non-EU
Russia	Non-EU
United States	Non-EU

Duration of Objective Response

DOR curves in each treatment group will be estimated using the KM product-limit method for subjects with a BOR of CR or PR. Median DOR, corresponding two-sided 95% CI, and range will be reported.

Time to Objective Response

Summary statistics of TTR will be provided by treatment group for subjects with a BOR of CR or PR. TTR curves will be estimated using the KM product-limit method in all randomized subjects and will represent the cumulative rate of response over time. For non-responders, subjects will be censored at the maximum time of response + 1 day of all subjects in their respective treatment group. Cumulative response rates will be tabulated at Week 12 and Month 6.

Other Analyses

The following subject-level graphics will be provided by treatment group.

- For responders only, the time course of the following events of interest will be graphically displayed: tumor response, tumor progression, last dose received, and death.
- For response-evaluable subjects (treated subjects with baseline and at least one on-study tumor assessment), a waterfall plot showing the best reduction in target lesion tumor burden based on investigator assessment.

7.5.2 Progression Free Survival

PFS curves for each treatment group will be estimated using the Kaplan-Meier (KM) product limit method in All Treated Subjects. Median PFS and corresponding two-sided, 95% confidence intervals will be computed. Descriptive HRs and corresponding two sided 95% CIs for Arm A relative to Arm B will be estimated using a Cox proportional hazards model, with treatment group as a single covariate, stratified by PD-L1 status and M Stage at screening (IVRS source). A p-value from a 2-sided log-rank test stratified by PD-L1 expression and M stage at screening will be presented for descriptive purposes. PFS rates at 6 months with 95% CIs will be estimated using KM methodology.

The source of progression event (death versus progression) will be summarized by treatment group.

The status of subjects who are censored in the PFS KM analysis will be tabulated for each treatment group using the following categories:

- On-study (on-treatment, in follow-up)
- Off-study (lost to follow-up, withdrawn consent, never treated)
- Received subsequent anticancer therapy

7.5.3 Overall Survival

OS curves for each treatment group will be estimated using the Kaplan-Meier (KM) product-limit method. Median OS and corresponding two-sided, 95% confidence intervals will be computed.

Descriptive HRs and corresponding two-sided 95% CIs for Arm A relative to Arm B will be estimated using a Cox proportional hazards model, with treatment group as a single covariate, stratified by PD-L1 status and M Stage at screening (IVRS source). No p-values will be presented for the OS endpoint.

The status of subjects who are censored in the OS KM analysis will be tabulated for each treatment group using following categories:

- on-study (on-treatment and not progressed, on-treatment progressed, in follow-up)
- off-study: (lost to follow-up, withdrew consent, etc)

Survival rates at 6 months will be estimated using KM estimates on the OS curve for each treatment group. Associated two-sided 95% CIs will be calculated.

7.5.4 Subject Follow-Up

The extent of follow-up defined as the time between randomization date and last known date alive (for subjects who are alive) or death date (for subjects who died) will be summarized descriptively (median, min, max) for all treated subjects in Arms A and B. A similar summary will be provided for all treated subjects in Cohort C, except that time will be measured from the first dosing date rather than the randomization date.

The currentness of follow-up, defined as the time between last OS contact (ie, last known date alive or death date) and data cut-off date, will be summarized by treatment group. Subjects who died before data cut-off date will automatically have zero value for currentness of follow-up. For subjects with last known date alive after data cut-off date, they will have zero value for currentness of follow-up as well. The currentness of follow-up will be categorized into the following categories: 0 days, 1-30 days, 31-60 days, 61-90 days, 91-120 days, 121-150 days, 151 or more days.

7.5.5 Subsequent Therapy

Subsequent therapy and response to subsequent therapy will be summarized and listed.

- Subsequent Therapy
 - Chemotherapy by drug name
 - Hormonal or biologic therapy by drug name
 - Immunotherapy (anti-PD1 agents, anti-PDL1 agents, anti-CTLA4 agents, and others) by drug name
 - BRAF inhibitor by drug name
 - MEK/NRAS inhibitor by drug name
 - Other investigational agent by drug name
 - Surgery
 - Radiotherapy
 - Any combination of the above
- By Subject Listing of Subsequent Therapy

7.5.6 Interim Analysis

Not applicable.

7.6 Safety

7.6.1 Rate of Drug-related Grade 3-5 AEs

For purposes of the primary endpoint analysis, the drug-related Grade 3 - 5 AE rate for All Treated Subjects in Arms A and B will be reported by treatment arm. Corresponding 95% CIs for the rate

in each treatment arm will be calculated using the Clopper-Pearson method. A p-value from a two-sided CMH test stratified by PD-L1 status and M Stage at screening (IVRS source) will be provided to compare the drug-related Grade 3 - 5 AE rate between the two treatment arms. Associated odds ratios and 95% CIs for Arm A relative to Arm B will be calculated. An estimate of the difference in rates (Arm A - Arm B) and corresponding 95% CI for the difference will be calculated using CMH methodology, adjusting for the same stratification factors.

Additional characterization of drug-related Grade 3-5 AEs will be provided, including summaries by system organ class (SOC) and preferred term (PT) during the entire treatment period and during the Part 1 treatment period and the Part 2 treatment period separately. These analyses are described further in Section 7.6.6.

7.6.2 Deaths

See Core Safety SAP¹. In addition, a separate death summary will be provided for the population of All Subjects Treated in Part 2.

7.6.3 Serious Adverse Events

See Core Safety SAP¹. Summaries of SAEs and drug-related SAEs with onset during the Part 2 treatment period (using the 30-day safety window only) will also be provided for All Subjects Treated in Part 2.

7.6.4 Adverse Events Leading to Discontinuation of Study Therapy

See Core Safety SAP¹. Summaries of AEs leading to discontinuation and drug-related AEs leading to discontinuation with onset during the Part 2 treatment period (using the 30-day safety window) will also be provided for All Subjects Treated in Part 2.

7.6.5 Adverse Events Leading to Dose Modification

See Core Safety SAP¹.

7.6.6 Adverse Events

See Core Safety SAP¹. Summaries of AEs and drug-related AEs will also be provided separately for events with onset during the Part 1 treatment period for All Treated Subjects and for events with onset during the Part 2 treatment period for All Subjects Treated in Part 2. These additional summaries by treatment period will be performed using the 30-day safety window only.

7.6.7 Select Adverse Events

See Core Safety SAP¹. In addition, the following analyses will be provided for events with onset during the Part 2 treatment period (using the 30-day safety window only) for All Subjects Treated in Part 2.

- Incidence of select AEs
- Incidence of drug-related select AEs

- Time-to resolution of select AE
- Time-to resolution of select AE where immune modulating medication was initiated
- Time-to resolution of drug-related select AE
- Time-to resolution of drug-related select AE where immune modulating medication was initiated

7.6.8 Immune Modulating Medication

See Core Safety SAP¹.

7.6.9 Multiple Events

See Core Safety SAP¹. In addition, a table showing the total number and rate (exposure adjusted) of occurrences for all AEs with onset during the Part 2 treatment period (using the 30-day safety window) will also be provided for All Subjects Treated in Part 2.

7.6.10 Other Events of Special Interest

See Core Safety SAP¹.

7.6.11 Immune-Mediated Adverse Events

See Core Safety SAP¹. Summaries of IMAEs with onset during the Part 2 treatment period and time to resolution of IMAEs with onset during the Part 2 treatment period will also be provided for All Subjects Treated in Part 2.

7.6.12 Laboratory Parameters

See Core Safety SAP¹. Lipase and Amylase will be added to the list of lab parameters to be summarized. The summaries for hematology, serum chemistry, and electrolytes will be repeated for results collected during the Part 2 treatment period for All Subjects Treated in Part 2.

7.6.13 Vital Signs and Pulse Oximetry

See Core Safety SAP¹.

7.6.14 Immunogenicity Analysis

See Core Safety SAP¹.

7.6.15 Pregnancy

See Core Safety SAP¹.

7.6.16 Adverse Events By Subgroup

See Core Safety SAP¹. Categories for region will be the same as those specified in [Section 7.5.1](#)

7.7 Pharmacokinetics

The nivolumab and ipilimumab concentration vs time data obtained in this study will be combined with data from other studies in the clinical development program to develop a population PK model. This model will be used to evaluate the effects of intrinsic and extrinsic covariates on the PK of nivolumab and ipilimumab to determine measures of individual exposure (such as steady state peak, trough and time-averaged concentration). Pharmacokinetic drug- drug interaction between nivolumab and ipilimumab will be studied by population PK approach as appropriate. Model determined exposures may be used for exposure-response analyses of selected efficacy and safety endpoints. The results of population PK, pharmacokinetic drug interaction and exposure response analyses will be reported separately, as needed.

7.8 Biomarkers

Analyses for PD-L1 from tumor tissue specimens, myeloid derived suppressor cells (MDSCs), serum cytokines, and peripheral T cell subsets are described below. Methodology for other biomarkers (including evaluation of the PET tracer [18F]-BMS-986192 as a biomarker for PD-L1 expression) will be detailed in a separate biomarker SAP.

7.8.1 PD-L1

Analyses of PD-L1 expression are descriptive in nature and intended to examine the distribution of PD-L1 expression and assess potential associations between PD-L1 expression and efficacy measures.

PD-L1 status is a categorical variable by X% cut off for quantifiable PD-L1 expression:

- High expression: $\geq X\%$ PD-L1 expression
- Low expression: $< X\%$ PD-L1 expression

where X denotes the PD-L1 expression cut-off of 1%, 5% and 10%. Additional cut off values may also be explored.

PD-L1 expression quartile is a quartilized variable of quantifiable PD-L1 expression from the pooled population.

Analyses of PD-L1 will include:

- Examine the distribution of PD-L1 expression
 - Assess potential association between PD-L1 expression quartile and PD-L1 status and efficacy measures
 - Assess potential association between PD-L1 expression quartile and PD-L1 status and overall AEs
- 1) Descriptive statistics of PD-L1 expression and PD-L1 status, analyses will be based on all PD-L1 evaluable subjects if not otherwise specified

- a) Listing of all PD-L1 IHC data, all PD-L1 tested subjects
 - b) Summary of tumor specimen acquisition and characteristics, all treated subjects
 - c) Summary statistics of PD-L1 expression by treatment groups of select subgroups, and overall.
 - d) Box plot of PD-L1 expression by treatment group and overall
 - e) Cumulative distribution plot of PD-L1 expression versus population percentile by treatment group and overall
 - f) Waterfall plots of individual PD-L1 expression by treatment group
 - g) Frequency of PD-L1 expression quartile and Status (X%), including indeterminate and unknown if over 5% of subjects fall in this category, by treatment group for select subgroups and overall, all PD-L1 tested subjects. Selected subgroups are identical to the subgroups used for ORR subgroup analysis ([Section 7.5.1](#)).
- 2) Evaluation of associations between PD-L1 expression quartile and PD-L1 status and efficacy measures. Analyses will be based all PD-L1 tested subjects if not otherwise specified. Each analysis will be performed for the subgroups listed below if not otherwise specified
- a) Each PD-L1 expression quartile subgroup
 - b) Each PD-L1 status subgroup
 - c) PD-L1 unknown or indeterminate subgroup

Analyses for ORR (BOR):

- Box plots of PD-L1 expression versus Response Status by treatment group

For each of the subgroups:

- Frequency and percentage of investigator-assessed BOR will be summarized for each treatment group.
- Investigator-assessed ORR will be computed by treatment group along with exact 95% CIs using the Clopper-Pearson method.

Analyses for PFS endpoint:

For each of the subgroups:

- PFS curves for each treatment group will be estimated using the Kaplan-Meier product limit method. Two-sided, 95% confidence intervals for median PFS will be constructed based on a log-log transformed CI for the survivor function.
- For Arms A and B, Forest plot of Hazard Ratios with 95% CIs

Analyses for OS endpoint:

For each of the subgroups:

- OS curves for each treatment group will be estimated using the Kaplan-Meier product limit method. Two-sided, 95% confidence intervals for median OS will be constructed based on a log-log transformed CI for the survivor function.

- For Arms A and B, Forest plot of Hazard Ratios with 95% CIs

3) Association of all AE and PD-L1 expression, all treated, PD-L1 tested subjects

Overall summary of any AEs by worst CTC grade (any grade, grade 3-4, grade 5) presented by SOC/PT by treatment group for following subgroups will be provided

- Each PD-L1 status subgroup (using 1% and 5% thresholds only)
- PD-L1 unknown or indeterminate subgroup.

7.8.2 Other Biomarkers

The following parameters and their corresponding change (or percent change) from baseline will be summarized for biomarker evaluable subjects by treatment arm and timepoint using descriptive statistics (N, mean, median, standard deviation, minimum, maximum):

- Peripheral T cells subsets (activated and proliferating CD4 and CD8 T cells: ICOS+CD3+CD4+, ICOS+CD3+CD8+, CTLA4+ CD3+CD4+, CTLA4+CD3+CD8+, PD-1+CD3+CD4+, PD-1+CD3+CD8+, ki67+ CD3+CD4+, ki67S+CD3+CD8+)
- MDSCs (myeloid-derived suppressor cells)
- Serum cytokines (with emphasis on interferon-gamma, interferon-gamma-stimulated cytokines: IFN-gamma, CXCL9, CXCL10)

A by-subject listing of these biomarkers measures will be provided.

7.9 Outcomes Research

7.9.2 *EuroQol EQ-5D*

Unless otherwise specified, the analysis of EQ-5D will be performed in all treated subjects who have an assessment at baseline and at least one or more post-baseline assessments.

Subject's overall health state on a visual analog scale (EQ-VAS) at each assessment time point will be summarized by treatment group using descriptive statistics (N, mean, SD, median, 25th and 75th percentiles,).

Proportion of subjects reporting problems for the 5 EQ-5D dimensions at each assessment time point will be summarized by level of problem and by treatment group. Percentages will be based on number subjects assessed at assessment time point.

EQ-5D questionnaire completion rate, defined as the proportion of questionnaires actually received out of the expected number (ie, number of subjects on treatment or in follow up), will be calculated and summarized for each assessment time point by treatment group.

A by-subject listing of EQ-5D with the problem levels for each of the 5 dimensions (mobility, self-care, usual activities, pain/discomfort and anxiety/depression), health state (5 dimensions digits combined in a 5-digit number) and EQ-VAS will be provided.

Results of EQ5D-Index will be presented separately and will be described in the GHEOR SAP.

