3.1.3 Follow-Up Phase

- Begins when the decision to discontinue a subject from study therapy is made (no further treatment with study therapy). Patients will be followed for efficacy and OS.
- Subjects who discontinue treatment for reasons other than tumor progression will continue to have tumor assessments beginning 12 weeks (± 1 week) after randomization and continuing every 8 weeks (± 1 week) for the first 12 months from randomization, and every 12 weeks (± 2 weeks) thereafter until documented tumor progression.

- Subjects will be followed for drug-related toxicities until these toxicities resolve, return to baseline or are deemed irreversible. All adverse events will be documented for a minimum of 100 days after last dose.
- After completion of the first two follow-up visits, subjects will be followed every 3 months for survival.

BMS may request that survival data be collected on all randomized subjects outside of the protocol defined window as detailed in the Time and Events [Table 5.1-4](#) Follow-up Assessments (CA209511). At the time of this request, each subject will be contacted to determine their survival status unless the subject has withdrawn consent for all contact.

The total duration of the study from start of randomization to primary analysis of the study is expected to be approximately 13 months (7 months of accrual + 6 months of follow-up after last subject has been dosed), assuming an accrual rate of 58 subjects per month. Additional survival follow-up may continue for up to 5 years from the primary analysis. The study will end once survival follow-up has concluded.

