Review of Concomitant Medications	X	
Laboratory Tests	X	Within 72 hrs prior to dosing to include CBC w/ differential, LFTs, BUN or serum urea level, creatinine, Ca, Mg, Na, K, Cl, LDH, Glucose, amylase, lipase, TSH (+ reflex Free T4 and Free T3), albumin if clinically indicated).
Pregnancy Test (WOCBP only)	X	Serum or urine within 24 hours prior to administration of first dose and every 3 weeks thereafter in Part 1 of the study.
Pharmacokinetic and Immunogenicity Assessments		
Immunogenicity blood sample	See Section 5.5 for details regarding specific sample timing	
PK Samples	See Section 5.5 for details regarding specific sample timing	

Table 5.1-2: On-Study Assessments Part 1 (CA209511)		
Procedure	For Part 1, Study Drug Every 3 Weeks for 4 Cycles (Both Arm A and Arm B)	Notes
	Cycle 1, 2, 3, 4 (Day 1)	
Exploratory Biomarker Testing		
Exploratory Serum Biomarkers	X	To be collected pre-dose; before first 4 combination doses only.
Peripheral Blood Mononuclear Cells (PBMCs)	X	To be collected pre-dose; before first 4 combination doses only. To be collected in USA and Canada only.
Whole Blood Sample (DNA)	X	X = before first combination dose only.
Myeloid-Derived Suppressor Cell (MDSCs)	X	To be collected pre-dose; before the first and the third combination dose only
Efficacy Assessment		
Tumor Assessment	See Notes	FIRST tumor assessment should be performed at 12 weeks (\pm 1 wk) following randomization. CT Chest, CT (or MRI) abdomen, pelvis and all known sites of disease. Use same imaging method as was used at screening/baseline. Subjects with a history of brain metastasis should have surveillance MRI approximately every 12 weeks, or sooner if clinically indicated

Table 5.1-2: On-Study Assessments Part 1 (CA209511)		
Procedure	For Part 1, Study Drug Every 3 Weeks for 4 Cycles (Both Arm A and Arm B)	Notes
	Cycle 1, 2, 3, 4 (Day 1)	
Outcomes Research Assessments		
EORTC QLQ-C30 and EQ-5D	X	To be completed at the start of the clinic visit every 6 weeks. First questionnaire should be completed after IRT randomization but before dosing. (Cycle 1, 3)
Health Care Utilization	X	Health Care Utilization will be collected at each visit
Clinical Drug Supplies		
IRT Drug Vial Assignment	X	Within 24 hours prior to dosing
Administer Study Treatment	X	First dose to be administered within 3 days following randomization. See Section 4.3 .

Table 5.1-3: On-Study Assessments - Part 2 (CA209511)		

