Tumor Assessment	See Notes	
First tumor assessment during Part 2 should occur after 8 weeks (\pm 1wk) relative to previous tumor assessment performed at week 12.
 
Subsequent tumor assessments should occur every 8 weeks (\pm 1 wk) for the first 12 months from randomization.
 
From the second year from randomization, tumor assessments should occur every 12 wks (\pm 2 wk) until disease progression.
 
CT Chest, CT (or MRI) abdomen, pelvis and all known sites of disease. Use same imaging method as was used at screening/baseline.
 
Subjects with a history of brain metastasis should have surveillance MRI approximately every 12 weeks, or sooner if clinically indicated.

Table 5.1-3: On-Study Assessments - Part 2 (CA209511)		
Procedure	For Part 2, Study Drug is Administered Every 4 Weeks (Both Arm A and Arm B)	Notes Cycle 5 will begin 6 weeks after Cycle 4
	Cycle 5 and beyond (Day 1)	
Clinical Drug Supplies		
IRT Drug Vial Assignment	X	
Administer Study Treatment	X	See Section 4.3 . Note: Within 3 days from vial assignment, the subject must receive the dose of study medication.

Table 5.1-4: Follow-up Assessments (CA209511)			
Procedure	Follow Up,^a Visits X1 and X2	Survival,^b Follow-up Y Visits	Notes
Safety Assessments			
Targeted Physical Examination	X		To assess for potential late emergent study drug related issues
Adverse Event Assessments	X	X	
Laboratory Tests	X		On site/local CBC w/differential, LFTs, BUN, creatinine, amylase, lipase and TSH (+ reflex Free T4 and Free T3) for X1, repeat at X2 if study drug related toxicity persists.
Pregnancy Test (WOCBP Only)	X		Serum or urine
Review of Concomitant Medications	X		
Pharmacokinetic Samples and Immunogenicity Assessments			
PK Samples	X		See Section 5.5 for schedule of assessments
Immunogenicity blood sample	X		Refer to Section 5.5 for details regarding specific sample timing
Survival Status			
Subject Status	X	X	Every 3 months, Survival Follow up Visits may be accomplished by visit or phone contact, to include subsequent anti-cancer therapy

Table 5.1-4: Follow-up Assessments (CA209511)			
Procedure	Follow Up,^a Visits X1 and X2	Survival,^b Follow-up Y Visits	Notes
Efficacy Assessments			

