Tumor Assessments	See Notes		
Only for subjects without progression on study therapy.
 
FIRST tumor assessment should first be performed at 12 weeks (± 1 wk) following randomization
 
SUBSEQUENT tumor assessments should occur every 8 weeks (± 1 wk) thereafter for the first 12 months, then every 12 wks (± 2 wk) until disease progression
 
CT Chest, CT (or MRI) abdomen, pelvis and all known sites of disease. Use same imaging method as was used at screening/baseline.
 
Subjects with a history of brain metastasis should have surveillance MRI approximately every 12 weeks, or sooner if clinically indicated

Exploratory Biomarker Testing			
Tumor Tissue Biopsy	X	X	Optional; collection upon progression

^a X visits occur as follows - X1 = 30 days from the last dose (± 7 days) or coincide with the date of discontinuation (± 7 days) if date of discontinuation is greater than 37 days after last dose, X2 = 84 days (± 7 days) from follow-up visit 1. Follow up visits X1 and X2 will occur only after patient completes all study treatment.

^b Y Survival visits = every 3 months from X2 (± 7 days).

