5.7 Outcomes Research Assessments

HRQoL will be assessed using the EORTC QLQ-C30. The EORTC QLQ-C30 is the most commonly used QoL instrument in advanced melanoma clinical studies. It is a 30-item instrument that has gained wide acceptance in oncology clinical studies. The EORTC QLQ-C30 comprises 6 functional scales (physical functioning, cognitive functioning, emotional functioning, social functioning and global quality of life) as well as nine symptom scales (fatigue, pain, nausea/vomiting, dyspnea, insomnia, appetite loss, constipation, diarrhea, and financial difficulties). Except for the overall health status and global quality of life items, responses for all items are 4-point categorical scales ranging from 0 (Not at all) to 4 (Very much). The overall health status/quality of life responses are 7-point Likert scales.

General health status will be measured using the EQ-5D. The EQ-5D is a standardized instrument for use as a measure of self-reported health status. The EQ-5D comprises 5 dimensions (mobility, self-care, usual activities, pain/discomfort and anxiety) and a visual analog rating scale (VAS). The utility data generated from the EQ-5D is recommended for and commonly used in cost effectiveness analysis.

The EQ-5D will be administered along with the EORTC QLQ-C30 during on-study phases (Parts 1 and 2) as outlined in [Section 5.1](#), to all subjects.

Healthcare resource utilization data (eg, hospitalizations, non-protocol specified medical visits, diagnostics, etc) will be collected for all randomized subjects. The resource utilization capture is specific to hospital admission utilization data and non-protocol specified visits related to study therapy. Resource utilization questions will be collected on-study phases (Parts 1 and 2) as outlined in [Section 5.1](#), to all subjects.

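### The EQ-5D completion rate counts subjects in follow-up as expected, although the supplied schedule for Arms A and B has no EQ-5D after treatment stops

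*SAP*

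**What the plan says.** SAP 7.9.2 plans an EQ-5D completion rate by time point and treatment group, "defined as the proportion of questionnaires actually received out of the expected number (ie, number of subjects on treatment or in follow up"). The same section makes its default EQ-5D population "all treated subjects who have an assessment at baseline and at least one or more post-baseline assessments", unless specified otherwise.

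The protocol places the instrument as follows:

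- Section 5.7: "The EQ-5D will be administered along with the EORTC QLQ-C30 during on-study phases (Parts 1 and 2) as outlined in" Section 5.1.
- Table 5.1-2 (Part 1): "First questionnaire should be completed after IRT randomization but before dosing. (Cycle 1, 3").
- Table 5.1-3 (Part 2): one form at each four-weekly visit from Cycle 5 through Cycle 11.
- Table 5.1-4 (follow-up): rows for safety, pharmacokinetics and immunogenicity, survival status, tumor assessment and biopsy. There is no EQ-5D or other outcomes-research row.

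Section 3.1.3 says of the follow-up phase: "Begins when the decision to discontinue a subject from study therapy is made (no further treatment with study therapy"). Section 3.1.2 lists the questionnaires under the treatment phase, which closes when study therapy is discontinued.

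**The concern.** A completion rate is read as the share of due forms that were returned. It tells the reader how far non-return could distort the questionnaire results. The SAP's denominator includes people who, under the schedule, had nothing to return. The rate would therefore fall as subjects come off therapy even with perfect compliance, and a reader could not separate missing forms from forms never planned. If one arm has more subjects in follow-up at a given time point, its rate would look worse for that reason alone. At stake is the meaning of one descriptive data-quality table.

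**Working it through.** **Step 1: the schedule.** Inputs are the Part 1 cycle length of 3 weeks, the 6-week interval from Cycle 4 to Cycle 5, and the Part 2 cycle length of 4 weeks (Protocol 4.5). In elapsed weeks from the first dose, without delays:

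- Cycles 1 to 4 fall at 0, 3, 6 and 9.
- Cycle 5 falls at 9 + 6 = 15.
- Cycles 6 to 11 fall at 19, 23, 27, 31, 35 and 39.

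The EQ-5D time points (Cycles 1, 3 and 5 to 11) are therefore at weeks 0, 6, 15, 19, 23, 27, 31, 35 and 39, which makes 2 + 7 = 9. The last, at week 39, agrees with the approximate week 40 end point in Protocol 3.1.2. None of the nine is a follow-up visit.

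**Step 2: the rate.** At one time point, let T be subjects on treatment (all due a form), F subjects in follow-up (none due a form) and c the proportion of due forms returned. Assume no unscheduled forms arrive from follow-up.

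- Forms received = c × T.
- SAP denominator = T + F.
- Reported rate = c × T/(T + F) = c × (1 − d), where d = F/(T + F).
- Rate with the denominator limited to subjects due = c × T/T = c.

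At the pre-dose Cycle 1 form F is 0 and the two agree. They separate as d grows at later time points.

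**Step 3: size.** The documents give neither d nor c. All values below are assumptions.

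| c | d = 10% | d = 30% | d = 60% |
|---|---|---|---|
| 100% | 90% | 70% | 40% |
| 90% | 81% | 63% | 36% |

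**Step 4: difference between arms.** With the same c in both arms, the reported gap is c × (d in B − d in A). The true gap is zero. Entries are reported rates for A vs B, with the gap in points.

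| Assumed d, A / B | c = 80% | c = 90% | c = 100% |
|---|---|---|---|
| 20% / 30% | 64.0% vs 56.0% (8.0) | 72.0% vs 63.0% (9.0) | 80.0% vs 70.0% (10.0) |
| 30% / 45% | 56.0% vs 44.0% (12.0) | 63.0% vs 49.5% (13.5) | 70.0% vs 55.0% (15.0) |
| 40% / 55% | 48.0% vs 36.0% (12.0) | 54.0% vs 40.5% (13.5) | 60.0% vs 45.0% (15.0) |
| 50% / 60% | 40.0% vs 32.0% (8.0) | 45.0% vs 36.0% (9.0) | 50.0% vs 40.0% (10.0) |

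For example, 0.90 × 0.70 = 63.0%, 0.90 × 0.55 = 49.5%, and the gap is 0.90 × (0.45 − 0.30) = 13.5 points.

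**Step 5: population.** If the default restriction quoted from SAP 7.9.2 governs this table, everyone in it has a baseline form, so baseline completion is 100% by construction. The completion sentence names no population of its own.

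**The case against.** The strongest defence is that the time points are cycle visits. A subject off therapy has no Cycle 7 visit, so only those still on treatment would be counted, and the words about follow-up would apply only to follow-up assessments. That reading is possible and harmless. But no follow-up EQ-5D is scheduled, so the phrase then has no content, and the SAP states it as the definition of the expected number. Two programmers could build different tables from it.

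The limits of the available text also count. SAP 4.2.4 (QLQ-C30 time windows), SAP 7.9.1, the Cohort C assessment schedule and the table mock-ups are not available here. A window rule in one of them might settle the matter, so the point is confined to the EQ-5D in Arms A and B as supplied. On population, it is fair to say that the default applies because nothing overrides it; a statement would still help.

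It is also true that the consequence is small. The EQ-5D dimension percentages use subjects assessed at each time point, the EQ-VAS summaries report N, and SAP 7.3.1 and 7.4.1 tabulate discontinuation and treatment duration by arm.

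Four stronger inferences are tempting and not supported:

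- *That Arm B's rate will be the one pulled down.* The planning rates of 40% and 55% are drug-related Grade 3 - 5 AE rates, not shares in follow-up.
- *That long survival follow-up magnifies the problem.* Protocol 3.1.3 says "Additional survival follow-up may continue for up to 5 years from the primary analysis", but the EQ-5D time points end at about week 40, so later follow-up adds none.
- *That per-subject completion is reported too low.* The SAP reports by time point and treatment group only.
- *That one week label for Cycle 5 is the right one.* Protocol 5.3 and Table 5.5.1-1 differ, and the answer depends on a week-counting convention that is not stated.

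**Conclusion.** The definition is wrong as written, with a minor effect. Against the supplied schedule for Arms A and B it understates completion by the factor T/(T+F), with no effect at the baseline form and more as subjects leave treatment. The illustrative range is a ceiling of 90% to 40% for follow-up shares of 10% to 60%. An artificial gap of 8 to 15 points between arms arises under the unequal shares shown. Both rest on assumed shares and on no forms being returned from follow-up.

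A reader might infer that the quality-of-life results are compromised. The documents do not support that. The HRQoL secondary endpoint is the QLQ-C30 (Protocol 8.3.2), whose SAP analysis section was not available and about which nothing is claimed. The primary endpoint, its power and the EQ-5D summaries do not use this denominator.

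**What to change.** In SAP 7.9.2:

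1. Define the expected number as subjects due an EQ-5D at that time point under the protocol schedule, that is, on treatment at that visit.
2. State which population the completion table uses, and whether the baseline-plus-post-baseline condition applies to it.
3. Show the number on treatment, by arm, beside the rate at each time point.

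The cost is one or two sentences and one table row. No new data are needed, and no result changes outside this table.

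As housekeeping, with no effect claimed, two items could be reconciled at the next protocol revision. Section 3.1.2 describes six-weekly questionnaires through month 6, which implies a week-12 form, while Tables 5.1-2 and 5.1-3 schedule none between Cycle 3 and Cycle 5. Section 5.3 and footnote a of Table 5.5.1-1 label Cycle 5 as Week 18 and Week 16 respectively.
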